13 SPECIAL INSTRUCTIONS

13.1 Dosimetric review

Treatment length and active length will be recorded for all patients. CT simulation shall be performed. Dose should be optimized to the cylinder as seen in Figure 1, Appendix D with dose normalized to 100% at the tip and at the midpoint of the active length. Dose at $\frac{1}{2}$ cm will be recorded.

14 ETHICAL AND REGULATORY CONSIDERATIONS

14.1 Informed consent

Informed consent will be obtained from all research participants prior to performing any study procedures using the most recent IRB approved version.

14.2 Institutional Review

Study will be approved by the Institutional Review Board of University of Utah.

14.3 Data and Safety Monitoring Plan

A Data and Safety Monitoring Committee (DSMC) is established at Huntsman Cancer Institute (HCI) and approved by the NCI to assure the well-being of patients enrolled on Investigator Initiated Trials that do not have an outside monitoring review. Roles and responsibilities of the DSMC are set forth in the NCI approved plan. The activities of this committee include a quarterly review of adverse events including SAEs, important medical events, significant revisions or amendments to the protocol, and approval of cohort/dose escalations. If the DSMC and/or the PI have concerns about unexpected safety issues, the study will be stopped and will not be resumed until the issues are resolved. The DSMC also reviews and approves audit reports generated by the Research Compliance Office.

This is a multicenter, phase III study classified as high risk per the NCI-approved DSM plan. Each high-risk study will be assigned a physician member of the DSMC as medical monitor, or in rare cases, an external medical monitor. The medical monitor will be notified of all serious adverse events (SAEs). Specific notifications will also be issued when a dose-limiting toxicity is encountered and when the MTD dose is defined. Approval of the medical monitor is required for all dose escalations. All serious adverse events (SAEs) occurring in patients treated at HCI or its affiliates will also be reviewed by the full DSMC monthly. The full committee will also review all toxicities for patients on treatment and less than or equal to 30 days of their last treatment on a quarterly basis.

Each high-risk study will also be assigned a dedicated research compliance officer who will monitor the trial. High-risk studies will be monitored by RCO personnel after the first patient is enrolled and every three months thereafter during active enrollment. The RCO monitor will review the study status and summarize enrollment, toxicities, SAEs, dose escalation, statistical endpoints (e.g., stopping rules), deviations, etc. for the full DSMC membership at the regularly scheduled meetings. Amendments that increase risk, change dosing, or impact study objectives will be reviewed by the DSMC and approved by the PRMC and IRB. High-risk trials will be formally reviewed by the DSMC after the first patient is enrolled and then quarterly thereafter.

An initial audit of high-risk studies will be conducted by the RCO approximately one year after enrollment begins and annually thereafter. Audits of high-risk studies may be conducted more frequently as requested by the DSMC, IRB, PRMC, RCO management, or the PI.

14.4 Adverse Events / Serious Adverse Events

This study will utilize the CTCAE (NCI Common Terminology Criteria for Adverse Events) Version 5.0 for AE and SAE reporting.

14.4.1 Adverse Events (AE)

An adverse event is the appearance or worsening of any undesirable sign, symptom, or medical condition occurring after starting the study drug even if the event is not considered to be related to study drug. For the purposes of this study, the terms toxicity and adverse event are used interchangeably. Medical conditions/diseases present before starting study drug are only considered adverse events if they worsen after starting study drug. Abnormal laboratory values or test results constitute adverse events only if they induce clinical signs or symptoms, are considered clinically significant, or require therapy.

Collection of adverse events will begin at start of brachytherapy and continue for 12 months after the start of brachytherapy.

Information about all adverse events, whether volunteered by the subject, discovered by investigator questioning, or detected through physical examination, laboratory test or other means, will be collected and recorded and followed as appropriate.

Adverse events should be evaluated to determine:

1. The severity grade based on CTCAE v.5.0 (grade 1-5).
2. Its relationship to the study treatment(s) (definite, probable, possible, unlikely, not related).
3. Its duration (start and end dates or if continuing at final exam).
4. Action taken (no action taken; study treatment temporarily interrupted; study treatment permanently discontinued due to this adverse event; concomitant medication taken; non-drug therapy given; hospitalization/prolonged hospitalization).
5. Whether it constitutes an SAE.

All adverse events will be treated appropriately. Such treatment may include changes in study drug treatment as listed in the dose modification section of this protocol (see section 6.1 for guidance). Once an adverse event is detected, it should be followed until its resolution, and assessment should be made at each visit (or more frequently, if necessary) of any changes in severity, the suspected relationship to the study drug, the interventions required to treat it, and the outcome.

All adverse events will be immediately recorded in the patient research chart.

14.4.2 Serious Adverse Event (SAE)

Information about all serious adverse events will be collected and recorded.

A serious adverse event is an undesirable sign, symptom or medical condition which:

- Is fatal or life-threatening
- Results in persistent or significant disability/incapacity
- Is medically significant, i.e., defined as an event that jeopardizes the patient or may require medical or surgical intervention to prevent one of the outcomes listed above
- Causes congenital anomaly or birth defect
- Requires inpatient hospitalization or prolongation of existing hospitalization, unless hospitalization is for:
 - Routine treatment or monitoring of the studied indication, not associated with any deterioration in condition (procedures such as central line placements, paracentesis, pain control).
 - Elective or pre-planned treatment for a pre-existing condition that is unrelated to the indication under study and has not worsened since the start of study drug.

- Treatment on an emergency outpatient basis for an event not fulfilling any of the definitions of a SAE given above and not resulting in hospital admission.
- Social reasons and respite care in the absence of any deterioration in the patient's general condition.

SAE evaluation will begin after the first treatment and will continue until the first follow up visit, 28 days (+/- 14) after the completion of study treatment. If the patient is unable to attend the first follow up visit, the SAE reporting period will be extended to 56 days after the completion of study treatment.

Any death from any cause while a patient is receiving treatment on this protocol or up to 30 days after the last dose of protocol treatment, or any death which occurs more than 30 days after protocol treatment has ended but which is felt to be treatment related, must be reported.

Toxicities which fall within the definitions listed above must be reported as an SAE regardless if they are felt to be treatment related or not. Toxicities unrelated to treatment that do NOT fall within the definitions above, must simply be documented as AEs in the patient research chart.

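### The SAE period in section 14.4.2 has no firm start or end, and for a patient seen early it closes before the protocol's own 30-day safety limits

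*Combined protocol and SAP*

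**What the plan says.** Four parts of the protocol bear on when a serious event counts as an SAE.

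- **Section 14.4.2, SAE period.** "SAE evaluation will begin after the first treatment and will continue until the first follow up visit, 28 days (+/- 14" days, counted from completion of treatment). For a patient who cannot attend that visit, "the SAE reporting period will be extended to 56 days after the completion of study treatment".
- **Section 14.4.1, AE period.** "Collection of adverse events will begin at start of brachytherapy and continue for 12 months after the start of brachytherapy". Each event is assessed on five items, the last being "Whether it constitutes an SAE".
- **Section 8, study calendar.** The first follow-up visit is at 1 month, plus or minus 12 weeks. AE assessments are scheduled at brachytherapy and at the 1, 6 and 12 month visits.
- **Sections 14.3 and 14.4.2, 30-day limits.** Deaths from any cause are reportable to 30 days after the last dose. Beyond that, "any death which occurs more than 30 days after protocol treatment has ended but which is felt to be treatment related, must be reported". The committee reviews all toxicities of patients on treatment and "less than or equal to 30 days of their last treatment on a quarterly basis".

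Section 14.4.2 also opens with a sentence that has no time limit: "Information about all serious adverse events will be collected and recorded".

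**The concern.** The start and the end of the SAE period each disagree with another section, and the end depends on when the patient happens to be seen.

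This matters because SAE status decides how fast an event is escalated. An SAE goes to the sponsor within one business day and on to the medical monitor (14.5). The full committee reviews it monthly (14.3), and all sites are told if it is unexpected and related (14.5). An event handled only as an AE is recorded in the patient research chart (14.4.1) and reaches the committee through quarterly review (14.3). Section 14.3 classes the trial as high risk. If sites apply the 14.4.2 period as written, the same serious event may be escalated for one patient and not for another, solely because of the visit date.

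**Working it through.** The plan gives no derived figure here, so the check is date arithmetic on the stated windows. Days count from completion of treatment unless stated otherwise.

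**1. Start.** AE collection starts with brachytherapy (14.4.1). SAE evaluation starts after the first treatment (14.4.2). Read literally, an event during the first insertion is an AE but precedes SAE evaluation. Read loosely, the two starts are the same. The text does not settle it.

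**2. End, by 14.4.2.**
- Earliest visit: 28 − 14 = day 14
- Latest visit: 28 + 14 = day 42
- Unable to attend: day 56

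**3. End, by the calendar.** Assume 1 month is 30 days; 12 weeks is 84 days.
- Latest visit: 30 + 84 = day 114
- Earliest visit: 30 − 84 = day −54, which is before treatment ends

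The calendar's upper limit is 114 − 42 = 72 days later than that of 14.4.2, and its lower limit cannot serve as an end to post-treatment observation. Day 42 is therefore not a firm limit for a site that works from the calendar.

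**4. Gap to the protocol's own 30-day limits.** For a patient seen on day v, with v below 30, the days between the end of the SAE period and day 30 number 30 − v.

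| Visit day | Days up to day 30 outside the SAE period |
|---|---|
| 14 | 30 − 14 = 16 (days 15 to 30) |
| 28 (nominal) | 30 − 28 = 2 (days 29 and 30) |
| 30 or later | 0 |

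For the patient seen on day 14, a death on day 20 must be reported. A non-fatal life-threatening event on day 20 lies outside the stated SAE period.

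**5. When such an event would next be asked about.** After the 1 month visit, the next scheduled AE assessment is at 6 months, plus or minus 12 weeks. With 30-day months, 180 − 84 = day 96 at the earliest and 180 + 84 = day 264 at the latest. An event on day 15 in a patient seen on day 14 might not be solicited for at least 96 − 15 = 81 days, unless she or her clinicians volunteer it.

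**The case against.** The best defence is that nothing need be missed. AEs are collected for 12 months from the start of brachytherapy and each is assessed for seriousness, so first-insertion events and events after an early visit should be in the database with a seriousness flag. Section 14.4.2 also requires toxicities meeting the definitions to be reported as SAEs whatever their cause, and 14.5 applies the one-business-day rule to all SAEs; neither sentence carries a time limit. The committee's 30-day toxicity review does not depend on SAE status. Deaths have their own rule. The stopping rule in 9.4 counts related grade 3 toxicities and is not tied to the SAE period.

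Most of this stands, and it rules out a reading in which the data are lost. It does not remove the inconsistency. The unlimited sentences share a section with a limited evaluation and reporting period, and up to six centers could reasonably follow different ones.

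Three stronger inferences are tempting, and the documents do not support them.

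- **Bias between arms.** A reader might note that the first insertion is 1 of 2 in the experimental arm and 1 of 3 to 5 in the control arm. Those are shares of insertions, not of events. Every patient has one first insertion, the end rule is the same in both arms, and AE collection runs 12 months in both. Section 10.1.5 reports adverse events as counts, proportions and exact intervals; no separate SAE comparison by arm is planned.
- **A fourfold difference in SAEs.** A reader might take 56/14 = 4 as the ratio of expected SAEs. That covers post-completion time only and sets the earliest visit against a missed one. The period also includes the rest of the course. At a constant hazard (itself an assumption), the ratio is (7 + 56)/(7 + 14) = 3.0 for a 7-day course, 70/28 = 2.5 for 14 days and 77/35 = 2.2 for 21 days.
- **Longer observation of the sickest.** The 56-day extension covers inability to attend for any reason, and calendar footnote 6 lets ill patients give questionnaires and history by telemedicine. A link with outcome is possible but not shown.

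**Conclusion.** The point holds as an inconsistency in safety reporting. The SAE period has an unclear start, an end that varies from day 14 to day 42 (56 if the patient cannot attend), and a calendar window that contradicts even those limits. For the earliest permitted visit under 14.4.2, it closes 16 days short of the protocol's own 30-day limits; for a visit on the nominal day 28, 2 days short.

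What is at risk is expedited reporting, medical monitor notification and monthly committee review of non-fatal serious events. The AE data themselves and the primary quality-of-life analysis are not affected. The number of events concerned cannot be estimated, because the documents give no SAE rate and no distribution of visit dates. The conclusion assumes that sites apply the stated SAE period literally; the calendar limits also assume a 30-day month. It is worth correcting because the plan provides for 80 patients in Cohort 2.

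**What to change.** Reconcile sections 8, 14.4.1 and 14.4.2 so that they give one SAE period and one visit window.

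1. Start the SAE period at the start of brachytherapy, as for AEs.
2. End it on one fixed day after the last fraction, the same for every patient, independent of the visit date and no earlier than day 30. Day 56, already used in 14.4.2, is one candidate.
3. Give the first follow-up visit a single window in both the calendar and 14.4.2.
4. For patients seen before the fixed day, check status on that day by phone or chart.
5. State whether serious events after that day, but within the 12 months of AE collection, still need one-business-day reporting.

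The cost is an amendment to the wording, a few more SAE reports, and a phone or chart check for patients seen early.

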14.5 SAE Reporting Requirements

All serious adverse events should be reported as soon as possible but no later than one business day after the Investigator becomes aware. All SAEs must be reported via the HCI CTMS (OnCore) and submitted to [contact]. The HCI Clinical Site Monitor will in turn, submit the report to the Medical Monitor. The RCO will summarize and present all reported SAEs according to the Data and Safety Monitoring Plan at the monthly DSMC meeting.

At a minimum, initial SAE reports must include a description of the event, assessment of event causality, event grade, and the expectedness of the event. Although the Investigator may not know all the information at the time of the event, the available information should be reported. An SAE follow-up may be submitted at a later date once more information is known. It is required that follow-up reports be submitted until the SAE is resolved.

The HCI DSMC will notify all participating sites of all unexpected and related SAEs via the Research Compliance Office (RCO). The RCO will also notify all investigators at remote clinical sites participating in a multisite trial of any other safety updates, including external safety reports, manufacturer's reports, and updates to the investigator's brochure.

Follow-Up Information

It is recommended that follow-up reports be submitted as new information becomes available, however, a follow-up report should be submitted within 3 days of knowledge of event resolution. Follow-up information will be added to the SAE in OnCore and submitted to the DSMC via RCO.

FDA Notifications:

- This study is IND exempt; therefore, there are no SAE reporting requirements to the FDA.

IRB Notification:

- Events meeting the University of Utah IRB or local IRB reporting requirements will be submitted per local guidelines.

14.6 Protocol Amendments

Any amendments or administrative changes in the research protocol during the period, for which the IRB approval has already been given, will not be initiated without submission of an amendment for IRB review and approval.

These requirements for approval will in no way prevent any immediate action from being taken by the investigator in the interests of preserving the safety of all patients included in the trial.

14.7 Protocol Deviations

A protocol deviation (or violation) is any departure from the defined procedures and treatment plans as outlined in the protocol version submitted and previously approved by the IRB. Protocol deviations have the potential to place participants at risk and can also undermine the scientific integrity of the study thus jeopardizing the justification for the research. Protocol deviations are unplanned and unintentional events.

Because some protocol deviations pose no conceivable threat to participant safety or scientific integrity, reporting is left to the discretion of the PI within the context of the guidelines below. The sponsor requires the **prompt reporting** to HCI RCO of protocol deviations which are:

- Exceptions to eligibility criteria.
- Intended to eliminate apparent immediate hazard to a research participant or
- Harmful (caused harm to participants or others, or place them at increased risk of harm - including physical, psychological, economic, or social harm), or
- Possible serious or continued noncompliance
- Participating external sites should follow their local IRB requirements regarding the reporting of protocol deviations

14.8 Clinical Trials Data Bank

The study will be registered on <http://clinicaltrials.gov> and the NCI CTRP (Clinical Trials Reporting Program) by the Clinical Trials Office.

16 APPENDICES

APPENDIX A. FIGO STAGING FIGO 2009 staging for carcinoma of the endometrium

Stage I* **Tumor confined to the corpus uteri**

stage IA* No or less than half myometrial invasion

stage IB* More than half myometrial invasion

Stage II* **Tumor invades cervical stroma, but does not extend beyond the uterus****

Stage III* **Local and/or regional spread of the tumor**

stage IIIA* Tumor invades the serosa of the corpus uteri and/or adnexae

stage IIIB* Vaginal and/or parametrial involvement

stage IIIC* Metastasis to pelvic and/or para-aortic lymph nodes

IIIC1* Positive pelvic lymph nodes

IIIC2* Positive para-aortic lymph nodes with or without pelvic nodes

Stage IV* **Tumor invades bladder and/or bowel mucosa, and/or distant metastasis**

stage IVA* Tumor invasion of bladder and/or bowel mucosa

stage IVB* Distant metastasis, including intra-abdominal metastases and/or inguinal lymph nodes

Either G1, G2 or G3 (G is FIGO grade) Endocervical glandular involvement only should be considered as Stage I and no longer as Stage II Positive cytology has to be reported separately, without changing the stage.

APPENDIX B. PERFORMANCE STATUS (WHO-ECOG)

Grade 0 Fully active, able to carry out all normal (pre-disease) activity without restriction

Grade 1 Restricted in physically strenuous activity but ambulatory and able to carry out light work, e.g., light house work, office work

Grade 2 Ambulatory and capable of all self-care but unable to carry out any work activities. Up and about more than 50% of waking hours

Grade 3 Capable of only limited self-care; confined to bed or chair more than 50% of waking hours

Grade 4 Completely disabled; cannot carry out any self-care; totally confined to bed or chair

APPENDIX C. HISTOLOGIC CLASSIFICATION AND GRADING SYSTEM International Society of Gynecologic Pathologists Classification for Endometrial Carcinomas

- Endometrioid adenocarcinoma
- Mucinous carcinoma
- Serous carcinoma
- Clear-cell carcinoma
- Squamous carcinoma
- Undifferentiated carcinoma
- Mixed types
- Miscellaneous carcinoma
- Metastatic carcinoma

Histologic classification of mixed carcinomas: Mixed serous and endometrioid carcinomas and mixed clear cell and endometrioid carcinomas should be classified as serous or clear cell carcinomas if they contain at least 10% of a serous or clear cell component, respectively, and otherwise be classified as endometrioid.

International Federation of Gynecology and Obstetrics (FIGO) and Armed Forces Institute of Pathology (AFIP) histologic grading system

G1 tumors have 5% or less of a nonsquamous or nonmorular solid growth pattern

G2 tumors have 6% to 50% of a nonsquamous or nonmorular solid growth pattern

G3 tumors have more than 50% of a nonsquamous or nonmorular solid growth pattern

A higher degree of nuclear atypia (in comparison with the architectural grade) raises the grade of a G1 or G2 tumor by 1.

Adenocarcinomas with squamous differentiation are graded according to the nuclear grade of the glandular component.

[figure not shown]
Where the treatment plan after hysterectomy is radiation with vaginal cuff brachytherapy without external beam, uterine sarcomas may be included.

APPENDIX D. VAGINAL BRACHYTHERAPY TREATMENT PLANNING AND DOSE REPORTING FORM

Figure 1 below shows a coronal schematic view of a standard vaginal cylindrical applicator, 3.5 cm in diameter, and 3.5 cm active length. Active length is the distance between the first (most cranial) and the last active source positions. All applicator points A are at the surface of the applicator. Applicator points A1 and A2 are located at the tip and on the side of the cylinder surface, respectively. Applicator points B1, and B2 are at 0.5 cm cranial and parallel to the central axis. Point A2 is half way the active length which, in this case, is 1.75 cm. Depending on the anisotropy of the source used, point A1 can receive a (5-10%) lower dose than the prescribed dose and point A2 a (5-10%) higher dose. The mean dose to points A1 and A2 should be 100%. **A2 and B2 should be measured at the half way point of the active length.**

Planned Treatment		Do you provide separate plans for each insertion?	
 Experimental Arm: 11 Gy at surface x 2 Fractions  Standard of Care Arm: 7 Gy at 0.5 cm x 3 Fractions  Standard of Care Arm: 5-5.5 Gy at 0.5 cm x 4 Fractions  Standard of Care Arm: 6 Gy at surface x 5 Fractions		 Yes*  No *If yes, provide a planning form for each fraction	
Treatment Start Date	A1 Dose	A2 Dose	
	cGy	cGy	
B1 Dose	B2 Dose	Active Treatment Length	
cGy	cGy	cm	
Additional Treatment Dates			

Figure 1.

Patient Initials: _____

Study ID: _____

Investigator Signature: _____

Date: _____

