Since publication of PORTEC-2, the most common fraction scheme for adjuvant vaginal brachytherapy for endometrial cancer is 7 Gy prescribed at $\frac{1}{2}$ cm (9.5 Gy at the vaginal surface for a 3 cm cylinder) delivered 3 times.¹⁶ This resulted in a vaginal control rate of >98%. Although the grade 3 vaginal toxicity rate was low at 1.9%, vaginal atrophy was reported in 40% of patients at 30 months. In the Sorbe randomized trial a significantly lower biologic effective dose was used and a vaginal control rate of >99% was achieved. Also, 6 Gy prescribed to the surface delivered 5 times was permitted in GOG 0249, an NCI-sponsored trial. The biologic effective dose with this regimen and the Sorbe et al., regimen of 2.5 Gy x 6 is significantly lower than the dose utilized in PORTEC-2 (Table 1). Two fractions of vaginal cuff brachytherapy of 11 Gy at the surface (7.3 Gy at $\frac{1}{2}$ cm) given weekly is a lower biologic effective dose than utilized in PORTEC-2, yet higher than utilized by Sorbe et al where vaginal control was >99%. Thus, lowering the dose compared to PORTEC-2 should result in more convenience, a lower rate of acute and late side effects, and not significantly impact vaginal control.

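### Appendix D and section 13.1 set 100% of the prescribed dose at the cylinder surface without limiting the rule to surface prescriptions, although two control schemes are prescribed at 0.5 cm

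*Combined protocol and SAP*

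**What the plan says.** Appendix D is a single treatment planning and dose reporting form. Its tick boxes cover the experimental scheme (11 Gy at the surface x 2) and all three control schemes. Two of the control boxes give a depth prescription: "Standard of Care Arm: 7 Gy at 0.5 cm x 3 Fractions" and "Standard of Care Arm: 5-5.5 Gy at 0.5 cm x 4 Fractions". The third, 6 Gy x 5, is at the surface. Section 6.1 and the study summary give the same depths.

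The text on the form describes a cylinder "3.5 cm in diameter, and 3.5 cm active length" and fixes the reference points: "All applicator points A are at the surface of the applicator". It measures them against the prescription: "point A1 can receive a (5-10%) lower dose than the prescribed dose and point A2 a (5-10%) higher dose". It then adds: "The mean dose to points A1 and A2 should be 100" per cent. Points B1 and B2 lie at 0.5 cm and their doses are recorded, but no percentage is set for them.

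Section 13.1 refers to Figure 1 of "Appendix D with dose normalized to 100% at the tip and at the midpoint of the active length". It names no arm and stands in the same paragraph as a sentence about recording lengths for all patients. Footnote 3 of the study calendar describes treatment in both arms and then sends the reader to Appendix D. In section 6.1 the same normalisation sentence appears only in the experimental-arm paragraph.

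**The concern.** Dose falls with distance from the cylinder, so one plan cannot deliver 100% of the prescription both at the surface and at 0.5 cm depth. The normalisation fits the two surface schemes. For a control patient on either 0.5 cm scheme, the ticked prescription and the normalisation sentence on the same form cannot both be met.

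Two things follow. A planner who took the sentence literally would deliver less than the prescribed control dose. A dosimetric reviewer who applied section 13.1 as written would query control plans that are in fact correct, and section 14.7 counts any departure from defined procedures as a deviation. Cohort 1 enrolment is complete (section 4.2), so only Cohort 2 can still be changed. It has 40 control patients planned, and the share who will receive a 0.5 cm scheme is not stated.

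**Working it through.** **Inputs**
- Surface dose for 7 Gy at 0.5 cm: section 3.1 gives "9.5 Gy at the vaginal surface for a 3 cm cylinder".
- Other surface and depth pairs for a 3 cm cylinder: the dose-seeking trial in section 3 used 5.0 and 2.5 Gy at 5 mm depth, and Table 1 lists 6.8 and 3.4 Gy at the surface.
- Cylinder in Appendix D: 3.5 cm diameter. The protocol gives no surface-to-depth ratio for this size.
- Stated allowance at A1 and A2: 5-10% in opposite directions.

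**Step 1: check the protocol's own figures.** With BED = n x d x (1 + d/(α/β)) and α/β = 3, three fractions of 9.5 Gy give 28.5 x (1 + 9.5/3) = 118.7 Gy; Table 1 has 119. EQD2 = 118.7/(1 + 2/3) = 71.2 Gy; Table 1 has 71. So Table 1 treats 7 Gy x 3 at 0.5 cm as 9.5 Gy x 3 at the surface.

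**Step 2: surface dose in a correct 0.5 cm plan, 3 cm cylinder.** 9.5/7 = 1.357, or about 136% of the prescription. The other pairs agree: 6.8/5.0 = 1.36 and 3.4/2.5 = 1.36.

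**Step 3: the 3.5 cm cylinder of Appendix D.** Assume dose falls as 1/distance from the central axis (an assumption, not in the documents).
- 3 cm cylinder: (1.5 + 0.5)/1.5 = 1.333, close to the documented 1.357.
- 3.5 cm cylinder: (1.75 + 0.5)/1.75 = 1.286, or about 129%.

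**Step 4: compare with the allowance.** The form lets A1 lie 5-10% below and A2 5-10% above the prescription, with a mean of 100%. The highest single-point value it allows is 110%, and the allowance cancels in the mean. Mean surface doses of 129-136% lie well outside it.

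**Step 5: effect of literal use.** With 100% set at the surface, every dose scales by the inverse of the ratio.
- 3 cm: 1 - 7/9.5 = 26.3% lower. For 7 Gy x 3, the total at 0.5 cm would be 21/1.357 = 15.5 Gy instead of 21 Gy.
- 3.5 cm (assumed fall-off): 1 - 1/1.286 = 22.2% lower.

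The same percentages apply to 5-5.5 Gy x 4.

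**The case against.** The strongest reply is that the treatment section already settles the matter. Section 6.1 places the surface normalisation only under the experimental arm and gives each control scheme its own depth. Section 13.1 looks like text carried over from that paragraph without its arm label; its reference to all patients concerns the recording of lengths. The sentence in Appendix D follows a remark on source anisotropy in the description of one schematic, so its purpose may be to balance tip against side. The form prints 0.5 cm beside the two schemes and records the A and B doses in cGy, so a misread plan would be visible. Figure 1 was not available to this review, and a label on it could limit the rule.

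Most of this stands as mitigation. It makes a misread plan unlikely, and it means the fault is a missing limit on a sentence. It does not remove the conflict. The form ties A1 and A2 to the prescribed dose, neither Appendix D nor section 13.1 limits the rule by scheme, and control patients are directed to this form.

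Two stronger figures are tempting:
- Section 3.1 pairs 11 Gy at the surface with 7.3 Gy at 0.5 cm. A reader might infer a surface dose of 151% (11/7.3 = 1.507) and a loss of about 34%. That pair has no stated cylinder size and disagrees with 9.5/7, which would give 11/1.357 = 8.1 Gy at 0.5 cm. It is not used here.
- A reader might also infer that the biological dose order of the arms is reversed. At α/β = 3, literal use of the rule in 7 Gy x 3 gives a surface EQD2 of 3 x 7 x (7 + 3)/(2 + 3) = 42 Gy, against 62 Gy for 11 Gy x 2 in Table 1. This describes a misreading that the rest of the protocol makes unlikely; it does not describe treatment as given.

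**Conclusion.** The concern holds as a fault in a written planning rule. Appendix D and section 13.1 state a 100% surface normalisation without limiting it to surface prescriptions, and it cannot be met together with two of the four schemes on the form. A correct 0.5 cm plan has about 136% at the surface (3 cm cylinder, the protocol's ratio) or about 129% (3.5 cm, assumed 1/distance fall-off). Literal use would lower the dose by about 26% or 22% respectively.

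A reader might infer that control patients have been underdosed, or that the Cohort 1 quality-of-life comparison was affected. The documents support neither. The 0.5 cm depth is explicit in the summary, in section 6.1 and on the tick boxes, and nothing shows that any plan followed the surface rule for a depth scheme. The Cohort 2 primary endpoint, the FACIT-COST score, is unaffected.

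The conclusion rests on the written description of Figure 1. The correction is worth making before further Cohort 2 controls are planned, particularly as up to five additional sites may take part.

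**What to change.** For Cohort 2, make the same change in section 13.1 and Appendix D:
- Limit the rule that A1 and A2 average 100% to the surface schemes, 11 Gy x 2 and 6 Gy x 5.
- State that for 7 Gy x 3 and 5-5.5 Gy x 4, 100% of the prescribed dose is at 0.5 cm depth, with A1 and A2 recorded only.

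There is no need to require that B1 and B2 average 100%. That would add a control-arm planning rule found nowhere in the protocol, and the text does not fully fix the position of B2.

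The cost is about one sentence in each place, with no new visit, procedure or data item. Optionally, a desk check can compare the A and B doses already recorded on control-arm forms with the ticked scheme. Its drawback is that it may reveal past deviations that then have to be handled and reported.
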